- i. Investigator must check for acute illness or body temperature $\geq 38.0^{\circ}\text{C}/100.4^{\circ}\text{F}$ at the time of vaccination. If the vaccination visit cannot be rescheduled within the allowed window or the contraindications to vaccination persist, the sponsor's medical monitor should be contacted for further guidance.
- j. If a situation arises where a study blood draw and vaccination with a licensed vaccine occur on the same day, the blood draw should be made before the vaccination.
- k. After vaccination, participants will remain under observation at the study site for at least 30 minutes. Any solicited local (at injection site) and systemic AEs, unsolicited AEs, SAEs, concomitant medications, and vital signs will be documented by study-site personnel following this observation period and participants will be allowed to leave the study site at approximately 45 minutes post-vaccination.
- l. Following the 28th day after each vaccination, only concomitant medications associated to SAEs will be recorded.
- m. If an event is still ongoing on Day 8 or Day 64 the participant should keep the diary after the review and collect information until resolution. The diary should be reviewed again at the next visit.
- n. The screening colposcopy will be performed as study procedure only if a result of colposcopy performed within last 12 months is not available.

AE=adverse event; d=day; FU=follow-up; HIV=human immunodeficiency virus; HR-HPV=high-risk human papillomavirus; ICF=informed consent form; immuno=immunology; mo=month; PBMC=peripheral blood mononuclear cell; PCR=polymerase chain reaction; PI=principal investigator; SAE=serious adverse event; SRCN=screening; SRP=study responsible physician

ABBREVIATIONS

Ad26	adenovirus serotype 26
AE	adverse event
AIS	adenocarcinoma in situ
BN	Bavarian Nordic (A/S)
CI	confidence interval
CIN	cervical intraepithelial neoplasia
CSR	Clinical Study Report
DNA	deoxyribonucleic acid
eCRF	electronic case report form
eDC	electronic data capture
EDTA	ethylenediaminetetraacetic acid
ELISA	enzyme-linked immunosorbent assay
ELISpot	enzyme-linked immunospot
ER	emergency room
EU	European Union
FAS	Full Analysis Set
FDA	Food and Drug Administration
FIH	First-in-Human
GCP	Good Clinical Practice
GLP	Good Laboratory Practice
β-hCG	β-human chorionic gonadotropin
HIV	human immunodeficiency virus
HPV	human papillomavirus
HR	high-risk
HSIL	high-grade squamous intraepithelial lesion
ICF	informed consent form

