To further characterize vaccine-elicited immune responses.	
These assessments will include, but are not limited to, the assessments described below. Some of the exploratory assessments will only be initiated if indicated by the secondary immunogenicity data.
 
Cell-mediated
 
 • Flow cytometry to characterize other cellular immune responses to the separate or combined protein peptide pools of HPV16 and HPV18 E2, E6 and E7 proteins, including, but not limited to, mucosa-homing markers, Th17, Th2, regulatory T cell (Treg), cytolytic markers, activation markers, and

Objectives	Endpoints
	
exhaustion markers.
 
 Transcriptome analysis to provide phenotypic and functional characterization of peripheral blood mononuclear cells (PBMCs) ex vivo or after stimulation with either HPV16 and/or HPV18 E2, E6, and/or E7 peptide pools. Enzyme-linked immunospot (ELISpot) assay to enumerate PBMCs able to produce IFNγ upon stimulation with HPV16 and/or HPV18 E2 (complete, N-terminal, or C-terminal), E6 and/or E7 protein peptide pools. ChipCytometry analysis of T cell responses to the separate or combined protein peptide pools of HPV16 and/or HPV18 E2, E6, and E7 proteins in PBMCs, including but not limited to CD4$^{+}$ and CD8$^{+}$ T cells producing IFNγ, TNFα and/or IL-2. 
Humoral
 
 Adenovirus neutralization assay to evaluate neutralizing antibody responses against the Ad26 vector. MVA neutralization assay to evaluate neutralizing antibody responses against the MVA vector. Antibody responses to the HPV16 and/or HPV18 capsid proteins L1 and/or L2 can be measured to investigate levels of HPV-specific antibodies before vaccination (not induced by vaccination with either Ad26.HPV16 or Ad26.HPV18), as well as induction of L1/L2 antibodies after vaccination as a “bystander” effect due to release of these proteins from infected cells after vaccine-mediated cytolytic T cell responses. L1/L2 antibodies to other HPV genotypes might also be measured. Antibody responses to E2, E6 and/or E7 of HPV16 and/or HPV18, or to these proteins of other HPV genotypes, can be evaluated.

Objectives	Endpoints

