
 To explore potential immune correlates for viral clearance. 	
 Immunogenicity endpoints of HPV-specific cellular or humoral responses described above, determined at multiple time points after vaccination will be used to explore potential immune correlates of viral clearance of HPV16 and/or HPV18.

^a The sum of women who clear an HPV16 infection plus women who clear an HPV18 infection

^b Women who receive CIN treatment will be considered as not clearing an HPV infection.

Refer to Section 9 for evaluations related to endpoints.

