3. STUDY DESIGN AND RATIONALE

3.1. Overview of Study Design

This is a multicenter, randomized, placebo-controlled, double-blind, safety, reactogenicity and immunogenicity Phase 1/2a study of 3 heterologous vaccine regimens with the Ad26.HPV16, Ad26.HPV18, and MVA.HPV16/18 recombinant vectors (Refer to Table 4). Vaccination will take place on Day 1 and Day 57. Study participants include approximately 66 women ≥ 18 to ≤ 60 years old with HPV types 16 or 18 infection of the cervix. This can be either persistent or recently diagnosed HPV infection, see Section 11.3 for definitions. Vaccination and safety monitoring among the HPV16 infected participants may occur independently from the HPV18 infected participants because the rate of enrollment of women with these 2 HPV types may differ as cervical HPV16 infections are more prevalent than HPV18 infections.

An Independent Data Monitoring Committee (IDMC) will be commissioned for this study to evaluate safety data over the course of the study and to review any event that meets a specific study pausing rule, stopping rule, or any other safety issue that may arise.

The IDMC will consist of members independent of the sponsor, including at least 1 medical expert in the relevant therapeutic area and at least 1 statistician. The IDMC responsibilities, authorities and procedures will be documented in its charter. The IDMC will review unblinded data (see Sections 11.8 and 11.9).

Randomization, vaccination and safety evaluations

The randomization, vaccination process and safety evaluations described below for HPV16 infected participants will be performed in the same manner and independently among HPV18 infected participants.

HPV16 infected participants ([Table 4](#) and [Figure 2](#)).

Dose 1 (Ad26-based)

Phase 1 (Dose Escalation)

- Step 1 [sentinels with low dose or placebo]: The first 2 participants (sentinels) will receive either a low dose Ad26.HPV16 (1 participant) or placebo (1 participant). Dosing of these 2 participants may occur on the same day depending on enrollment rates. Vaccination of additional participants will be halted until a 24-hour and 7-day post vaccination blinded safety review of solicited and unsolicited AEs are performed by the principal investigator (PI) and the sponsor's study responsible physician (SRP).

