4.2. Exclusion Criteria

Any potential participant who meets any of the following criteria will be excluded from participating in the study:

1. in case cytology results are available, participant has current or history of HSIL, AIS or any high-grade vulvar, vaginal or anal intraepithelial neoplasia.
2. current or history of CIN2+ or cervical cancer.
3. confirmed co-infection with both HPV16 and HPV18.
4. Criterion modified per Amendment 3:

4.1 acute illness (this does not include minor illnesses such as diarrhea or mild upper respiratory tract infection) or temperature $\geq 38.0^{\circ}\text{C}$ within 24 hours prior to the first dose of study vaccine; enrollment at a later date is permitted.

Note: Before vaccination, the investigator must check for any symptoms of an acute illness or oral temperature $\geq 38.0^{\circ}\text{C}$. If the randomization visit cannot be rescheduled within the allowed screening window or the contraindications to vaccination persist, the sponsor should be contacted for further guidance.

5. history of an underlying clinically significant acute or chronic medical condition, other than infection with HPV, or physical examination findings for which, in the opinion of the investigator, participation would not be in the best interest of the participant (eg, compromise the well-being) or that could prevent, limit, or confound the protocol-specified assessments.
6. had major surgery (per the investigator's judgment), within 12 weeks before first vaccination, or will not have fully recovered from surgery, or has surgery planned within 6 months after the last dose of study vaccine.

Note: Participants with planned surgical procedures to be conducted under local or locoregional anesthesia and not judged as major by the investigator may participate.

7. tests positive for HIV at screening.
8. chronic active hepatitis B or hepatitis C infection, verified at screening by hepatitis B surface antigen or anti-hepatitis C virus antibody, respectively.
9. vaginal atrophy with or without topical hormonal therapies or systemic selective estrogen receptor modulators.
10. exposed to at least 1 dose of an HPV prophylactic vaccine or participant has participated in the past in another preventive or therapeutic HPV vaccine study.
11. clinically significant gynecological abnormalities that could, in the judgment of the investigator, interfere with study evaluation (eg, prolapse, myoma, fibroid, hysterectomy).
12. Criterion modified per Amendment 3:

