8. PRE-STUDY AND CONCOMITANT THERAPY

Pre-study specific therapies such as analgesic/antipyretic medications and non-steroidal anti-inflammatory drugs (NSAIDs), administered up to 30 days before first vaccination must be recorded at screening.

Concomitant therapies must be recorded from the time of ICF signature through 28 days after each vaccination, and additionally outside of these periods when associated with an SAE meeting the criteria outlined in Section 12.3.2. Information on concomitant use of herbal supplements or vitamins will not be collected.

Use of any experimental medication (including experimental vaccines other than the study vaccine) during the study is not allowed. Participants may not receive an investigational drug or use an investigation medical device within 30 days or receive an investigational vaccine within 6 months before the planned administration of the first dose of study vaccine.

Vaccination with licensed live-attenuated vaccines within 28 days of a study vaccination (ie, before and after) is not allowed. Other licensed vaccines (eg, tetanus, hepatitis A, hepatitis B, rabies) should be given at least 14 days before (or at least 14 days after) administration of study vaccine. If a vaccine is indicated in a post-exposure setting (eg, rabies or tetanus), it must take priority over the study vaccine.

Participants can receive medications such as acetaminophen, NSAIDs, or antihistamines as needed, although their use must be documented and use of these medications as routine prophylaxis prior to study vaccination is discouraged.

Chronic (longer than 10 days) or recurrent use of immunomodulators/suppressors, eg, cancer chemotherapeutic agents, systemic corticosteroids is prohibited during the study and within 6 months before the planned administration of the first dose of study vaccine (Note: Ocular, topical or inhaled steroids are allowed). Antineoplastic and immunomodulating agents, including herbal products, or radiotherapy are prohibited during the study and within 6 months before the planned administration of the first dose of study vaccine. If chronic use of such medicines becomes medically indicated during the course of the study for any participant, the sponsor

should be contacted. The participant should remain in the study but should not receive further study vaccination^a.

The sponsor must be notified in advance (or as soon as possible thereafter) of any instances in which prohibited therapies are administered.

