9.2. Study Evaluations

9.2.1. Safety

An IDMC will be commissioned to evaluate safety data over the course of the study and to review any events that meet a specific study pausing or stopping rule or any other safety issue that may arise. Details regarding the IDMC are provided in Section [11.8](#).

Any clinically relevant changes occurring from the signing of the ICF until 28 days after the first vaccination and from the second vaccination through the following 28 days must be recorded on the AE section of the eCRF. Outside these periods, reporting will be limited to all SAEs.

Any clinically significant abnormalities (including those persisting at the end of the study/early exit) will be followed by the investigator until resolution or until a clinically stable endpoint is reached. All AEs and laboratory data will be coded for severity according to the criteria presented in Section [12.1.3](#) (see [Attachment 2](#)).

The PI, together with the sponsor's SRP, will be responsible for the safety monitoring of the study, and will halt vaccination of further subjects in case any of the pre-specified pausing or stopping rules described in Section [11.9](#) have been met.

The study will include the following evaluations of safety and reactogenicity according to the time points provided in the [Time and Events Schedule](#):

Adverse Events

All AEs will be reported as specified in Section 12.

For solicited AEs, the following applies.

Solicited Adverse Events

After each vaccination, participants will remain under observation at the study site for at least 30 minutes for presence of any acute reactions and solicited events. In addition, participants will record solicited symptoms in a diary for 7 days post-vaccination. All participants will be provided with a diary and instructions on how to complete the Diary (Section 9.1.1). Diary information will be transcribed by the study personnel in the diary eCRF pages. Once a solicited symptom from a diary is considered to be of severity Grade 1 or above, it will be referred to as a solicited AE.

Solicited Injection Site (Local) Adverse Events

Participants will be asked to note in the diary occurrences of pain/tenderness, erythema and induration/swelling at the study vaccine injection site daily for 7 days post-vaccination (day of vaccination and the subsequent 7 days). The extent (largest diameter) of any erythema, and induration/swelling should be measured (using the ruler supplied) and recorded daily.

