9.2.3. Virology and Histology

HPV16 and HPV18 genotyping will be performed with a qualitative PCR test (Cobas[®], Roche) on the cervical samples. Prior to vaccination, a participant will have a confirmed diagnosis of an HPV16 or HPV18 infection. More information on the identification of an HPV infection is provided in the flow chart (Figure 4).

Cervical samples will be collected by the healthcare provider and by the participant (self-sampling) at the time points indicated in the [Time and Events Schedule](#). Healthcare provider-obtained cervical samples collected using an endocervical brush will be processed in a transport medium and send to the central laboratory. Participants will self-collect cervico-vaginal samples with a dry self-sampling device (Evalyn[®] Brush, Rovers Medical Devices) at the study site. Immediately after collection of the cervico-vaginal specimen for this study, the Evalyn[®]

Brush should be dispensed in ThinPrep® following the procedure described in the Laboratory Manual. After collection of the cervico-vaginal sample, the dry Evalyn® Brush will be suspended in transport medium at the study site and sent to the central laboratory.

Cobas® testing will be performed by a central sponsor designated laboratory.

A quantitative HPV PCR genotyping test that detects HPV16 and HPV18 together with other individual HR-HPV types will be used on all cervical samples (healthcare provider-collected and self-collected) to address the exploratory endpoints.

Colposcopy examination will occur during screening only for those participants who do not have recent (within the last 12 months) examination results. A mandatory colposcopy examination will occur 12 months after the first dose for all participants. All colposcopy biopsy specimens will be sent to a central laboratory for standardized interpretation. Histopathological reports on biopsy and excision specimens will classify findings as: negative, CIN1, CIN2, CIN3, AIS and invasive malignancy. Note: All participants will have HSV-2 serology testing on the day of the first vaccination and the 12-month follow-up visit (or the early exit visit, if applicable).

Should a participant have an examination or treatment with a non-study gynecologist, she will be asked if she consents to allow study staff to access her medical records and obtain slide and tissue for evaluation.

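### The clearance endpoint scores women who receive CIN treatment as non-clearers, but no visit asks about such treatment, and licensed HPV vaccine given late in follow-up also goes unrecorded

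*Protocol*

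**What the plan says.** Protocol Section 2.1 (and the Synopsis) defines viral clearance as a negative genotype result for the baseline HPV type over the study period. Footnote b adds: "Women who receive CIN treatment will be considered as not clearing an HPV infection". The CIN1-regression endpoint requires clearance in the same sense, and the immune-correlate objective uses clearance as its outcome.

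The recording rules are narrower in time:

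- Section 8: "Concomitant therapies must be recorded from the time of ICF signature through 28 days after each vaccination". Beyond that, therapies are recorded only when linked to an SAE.
- Time and Events Schedule, footnote l: "Following the 28th day after each vaccination, only concomitant medications associated to SAEs will be recorded".
- Section 9.2.1, on clinically relevant changes after the two 28-day periods: "Outside these periods, reporting will be limited to all SAEs".
- Sections 9.1.4.2 and 9.1.4.3: Visits 11, 12, 13 and 14 list SAEs and SAE-related medication only.
- Section 9.2.3: "Should a participant have an examination or treatment with a non-study gynecologist, she will be asked if she consents to allow study staff" to see her records and obtain slides and tissue. This provision has no time limit.

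On licensed HPV vaccine, exclusion criterion 10 (Section 4.2) bars women "exposed to at least 1 dose of an HPV prophylactic vaccine" before entry. For the study period, Section 8 sets only a 14-day spacing from study doses for licensed vaccines that are not live, and does not name HPV vaccine. Among the optional humoral assessments, Section 2.1 lists pre-vaccination levels "as well as induction of L1/L2 antibodies after vaccination as a" bystander effect of vaccine-induced killing of infected cells.

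**The concern.** Footnote b makes one exposure decisive for an endpoint. If that exposure is not collected systematically, the rule cannot be applied as written, and a statistical analysis plan cannot supply data that were never gathered. The error also runs against the rule. Removing infected epithelium may turn the PCR negative, so an unknown treated woman counts as cleared instead of not cleared. If she had CIN1 at baseline and a normal colposcopic impression at Week 52, she also counts as regressed, and her status enters the immune-correlate analysis.

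The L1/L2 reading has a similar weakness. Section 1.1 says licensed HPV vaccines work by inducing antibody to L1. A dose during follow-up could therefore raise the same quantity that the endpoint would attribute to the study vaccine.

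**Working it through.** **Inputs.** Doses: "Vaccination will take place on Day 1 and Day 57" (Section 3.1). Last visit: Day 366 ± 14. Recording window: 28 days after each dose (Section 8). Planned arm sizes per HPV type (Table 4): 4 in Regimen 1, 10 in Regimen 2, 10 in Regimen 3, 9 on placebo. The protocol states no coverage figure, so there is none to reproduce.

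**Step 1: share of follow-up outside the window.**

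- Inside: Days 1–29 (29 days) + Days 57–85 (29 days) = 58 days.
- Outside: Days 30–56 (27 days) + Days 86–366 (281 days) = 308 days; 308/366 = 84.2%.
- Counted as elapsed time: 1 − 56/365 = 84.7%.
- With Visit 14 at Day 352 or Day 380: 1 − 58/352 = 83.5%, or 1 − 58/380 = 84.7%.
- Counting a full 42-day screening period as covered: 1 − 100/408 = 75.5%.

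About 84% is therefore stable for follow-up after the first dose.

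**Step 2: which samples are affected.** Visits 11 (Day 113), 12 (Day 183), 13 (Day 239) and 14 (Day 366) all fall in the second gap, and each takes a self-collected PCR sample. For the samples on Day 57 and Day 78, only Days 30–56 are uncovered.

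**Step 3: routes by which CIN treatment in the gap could reach the database.**

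| Route | Reach in the gap | Limit |
|---|---|---|
| Concomitant therapy (Section 8) | None | SAE-linked only |
| Non-serious AE (9.2.1) | None | 28-day windows |
| SAE (12.1.1, 12.3.2) | Whole study | An outpatient procedure without hospitalization qualifies only if judged medically important or if another seriousness criterion is met |
| Notification of prohibited therapy (Section 8) | Whole study | Antineoplastic and immunomodulating agents and radiotherapy; not excision or ablation |
| Outside gynecologist (9.2.3) | Whole study | Non-study provider; consent; the site must learn of it; no link to footnote b |

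Section 9.2.3 also classifies excision specimens, but ablation leaves none. No row is a scheduled question.

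**Step 4: effect of one misclassified woman.** The change in an arm's clearance proportion is 1/n.

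- n = 10: 10 points; n = 9: 11.1 points; n = 4: 25 points.
- HPV types pooled: n = 20: 5 points; n = 18 (placebo): 5.6 points; n = 8 (Regimen 1): 12.5 points.

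Section 11.6 also analyzes by infection type, which makes the cells smaller still.

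**Step 5: licensed HPV vaccine.** Criterion 10 looks back from entry, and Section 8 controls only spacing. After Day 85 a dose with no related SAE has no planned record, while serum is still due at Week 52. Section 1.1 says these vaccines are not indicated above age 26, so the issue mainly concerns the younger part of the 18-to-60 range, all unvaccinated at entry under criterion 10.

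**The case against.** The strongest reply is that 84% measures the wrong thing. A reader might infer that CIN treatment goes unrecorded for 84% of follow-up, and the documents do not support that. The figure describes the general therapy and AE window. Section 9.2.3 applies throughout, some drug treatments must be notified as prohibited therapy, and some procedures could be reported as medically important SAEs. This stands, and it limits the claim to the absence of systematic capture.

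The scenario is also narrow. Current or past CIN2+ is excluded. The only mandated colposcopy after dosing is at Week 52, together with the last virology sample, so treatment it prompts comes too late to affect that sample. Earlier treatment would come mainly from outside care, which is the case Section 9.2.3 addresses. It is still foreseeable: Section 1.2.4 gives treatment on progression as standard of care, and the entry colposcopy may be up to 12 months old.

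Two further inferences go too far. One is that treatment would be more common on placebo, so that the error hides a vaccine effect; the protocol gives no treatment rate by arm or overall. The other is that an L1 rise from a licensed vaccine cannot be told from the bystander effect. Section 1.1 says all three licensed vaccines target both HPV16 and HPV18, while confirmed co-infection with both is an exclusion. Antibody to the non-infecting type could therefore help separate the two, if it is measured. Measuring both types is optional.

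It can also be said that Section 4.3 arguably carries criterion 10 into the study period, and that the eCRF, which is not shown, may hold a suitable field. Neither is stated. The protocol's own visit lists and recording limits point the other way.

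**Conclusion.** The point holds as a gap in data collection. Footnote b depends on an exposure that no visit asks about, and Visits 11 to 14 lie in the 308 days when only SAEs and SAE-related medication are recorded. The remaining general route, through Section 9.2.3, is conditional and not connected to the footnote. A treated, PCR-negative woman could be scored as cleared, and as regressed if she had CIN1 at baseline.

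One such woman is worth 10 to 11 points in an arm of 9 or 10, and 25 points in an arm of 4, at the planned sizes for one HPV type. This is a per-woman effect, not an expected bias; the number of treated women cannot be derived from the protocol. The HPV-vaccine gap is real but smaller, because the L1/L2 measurement is optional.

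Every affected analysis is exploratory and descriptive. No primary or secondary endpoint, sample-size statement or error rate changes. The change is worth making because it is cheap and lets the stated rule be applied.

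**What to change.** In Section 8, the Time and Events Schedule and Sections 9.1.4.1 to 9.1.4.4, add two questions at Visits 6, 9 and 11 to 14 and at early exit, covering ICF signature to Week 52 regardless of SAE status:

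1. Date and type of any CIN treatment, by study or non-study providers.
2. Date and type of any licensed HPV vaccine.

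State in footnote b that the non-clearer rule is applied from the first record. State that L1/L2 samples taken after a licensed HPV vaccine are flagged or excluded.

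This records exposure only and does not alter what care is allowed. The cost is two eCRF questions at existing visits and a short addition to the sections named, with no new visit or procedure. A few late L1/L2 values may be dropped.
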